Appendix 2 – Karnofsky Performance Status Scale

KARNOFSKY PERFORMANCE STATUS SCALE Definitions of Rating Criteria (%)

The Karnofsky Performance Scale Index allows patients to be classified in terms of their functional impairment. (16, 8). This can be used to compare effectiveness of different therapies and to assess the prognosis in individual patients. The lower the Karnofsky score, the worse the survival for most serious illnesses.

		Normal no complaints; no evidence of disease.
Able to carry on normal activity and to work; no special care needed.	90	Able to carry on normal activity; minor signs or symptoms of disease.
	80	Normal activity with effort; some signs or symptoms of disease.
	70	Cares for self; unable to carry on normal activity or to do active work.
Unable to work; able to live at home and care for most personal needs; varying amount of assistance needed.		Requires occasional assistance, but is able to care for most of his personal needs.
	50	Requires considerable assistance and frequent medical care.
	40	Disabled; requires special care and assistance.
Unable to care for self; requires equivalent of	30	Severely disabled; hospital admission is indicated although death not imminent.
institutional or hospital care; disease may be progressing rapidly.		Very sick; hospital admission necessary; active supportive treatment necessary.
	10	Moribund; fatal processes progressing rapidly.
	0	Dead.

Confidential Page 74 of 83

Appendix 3 - Laboratory Tests

Laboratory Tests and Methods

All laboratory assessments will be described in a laboratory manual. Laboratory technicians have received specific training on these standard methods.

Biochemical tests

14 parameters will be analysed:

Albumin	Calcium
Alkaline phosphatase	Glucose
Alanine aminotransferase	Bicarbonates
Aspartate aminotransferase	Blood urea nitrogen
Total bilirubin	Sodium
Total protein	Chloride
Creatinine	Potassium

Haematological tests

- Haemoglobin assay
- White blood cells: count and differential count
- Platelets: count
- Microscope: full blood cell count (visual count) (see Investigator Manual)

Urine analysis

Urine dipsticks for laboratory safety analyses / Combur 9 Test®

White blood cells	Nitrites
рН	Glucose
Protein	Ketone bodies
Urobilinogen	Bilirubin
Blood	Haemoglobin

• Urine pregnancy test

CSF analysis (see Investigator Manual)

- Modified Single Centrifugation (MSC): detection of parasites
- Counting chamber: WBC count

Blood parasitology tests (see Investigator Manual)

- Thick/thin blood smears
- Woo test /CTC
- mAECT
- mAECT-BC

Confidential Page 75 of 83

Quantities of biological fluids required at each sampling timepoint

Screening Visit (Day -15 to Day -1)

	Type of test	Specific test	Number of samples	Quantity per sample (approx.)	Total quantity		
		Woo/CTC	1	100 μL			
	Parasitology	Thin/thick blood smear	1	≤ 300 µL	≤ 400 µL		
		mAECT (±BC)	1	5 mL	5 mL		
Blood		Haemoglobin	1	20 μL			
	Haematology	WBC	1	20 µL	170 µL		
	,	Platelet count	1	10 μL	(capillary blood ¹⁾		
		Differential WBC	1	20 µL	blood '		
	Biochemistry	14 parameters	1	100 µL			
Lymph	Parasitology	If lymph nodes detectable					
CSF	Parasitology	Modified Single Centrifugation	1	4 mL	4 mL		
Urine	Pregnancy		1	5 mL	10 ml		
Orine	Urine analysis	Combur 9 Test®	1	5 mL	10 mL		

End-of-Treatment Visit (Day 11)

	Type of test	Specific test	Number of samples	Quantity per sample (approx.)	Total quantity	
		Woo/CTC	1	100 μL		
	Parasitology	Thin/thick blood smear	1	≤ 300 µL	≤ 400 µL	
		mAECT (±BC)	1	5 mL	5 mL	
Blood	Haematology	Haemoglobin	1	20 µL		
		WBC	1	20 µL	170 µL	
		Platelet count	1	10 μL	(capillary	
		Differential WBC	1	20 µL	blood ¹⁾	
	Biochemistry	14 parameters	1	100 μL		
Lymph	Parasitology	If lymph nodes detectable				
Urine	Pregnancy		1	5 mL	40	
Offile	Urine analysis	Combur 9 Test®	1	5 mL	10 mL	

Confidential Page 76 of 83

Follow-up Visits at 3, 6, 12 and 18 months (per visit)

	Type of test	Specific test	Number of samples	Quantity per sample (approx.)	Total volume per visit
		Woo/CTC	1	100 µL	
	Parasitology	Thin/thick blood smear	1	≤ 300 µL	≤ 400 µL
		mAECT (±BC)	1	5 mL	5 mL
Blood		Haemoglobin	1	20 µL	
Біооц	Haematology (M3 and M6)	WBC	20 µL	170 ul	
		Platelet count	1	10 µL	170 μL (capillary
		Differential WBC	1	20 µL	blood ¹⁾
	Biochemistry (M3 and M6)	14 parameters	1	100 µL	
Lymph	Parasitology	If lymph nodes detectable			
CSF	Parasitology	Modified Single Centrifugation	1	4 mL	4 mL
Urine	Pregnancy (M3 and M6)		1	5 mL	5 mL

Quantity of blood required for PK analyses

Entire study

	Type of test	Number of samples	Quantity per sample (approx.)	Total volume
Blood	PK	6	2mL	12 mL

All haematological and biochemical analyses can be performed using a single finger-prick with a Tenderlett® device or similar.

Confidential Page 77 of 83

Appendix 4 - Study Schedule

Final protocol available	August 2016
IMP available	October 2016
First patient first visit	November 2016
Duration of recruitment period	36 months
Duration of follow-up period	18 months
Last patient last visit	1st quarter 2021
Final clinical study report	3rd quarter 2021

Organisation of Study

[figure not shown]
Country	DRC and Guinea			
Planned number of patients	174 patients			
Number of sites	At least 4 sites			
Number of patients per site	Between 20 and 50			
Role of DSMB	A DSMB will be appointed, in charge of safety issues in the same way as for study DNDiFEX004.			
Role of partners	Ministry of Health, Kinshasa, DRC • Principal Investigator PNLTHA, Kinshasa, DRC • Supervision of investigational site teams • Coordination of supplies and active screening teams IRD and PNLTHA in Guinea • Supervision of investigational site teams • Coordination of supplies and active screening teams			
Other particular needs	Mobile teams for active case screening Equipment and supplies for biochemical and haematological analyses Telecommunication facilities and computing equipment			

Confidential Page 78 of 83

Appendix 5 - Packaging of IMP

[figure not shown]
Mock-up of Packaging

a. Adults and children with body weight 35 kg or more

Confidential Page 79 of 83

b. Children with body weight less than 35 kg

Confidential Page 80 of 83

Appendix 6 - CTCAE version 4.03 adapted

	CTCAE vs 0 SOC	CTCAE v4.0 Term	units	IIN	IIIN	Grade 1	Grade 2	Grade 3	Grade 4	Grade 5	CTCAE v4.0 AE Term Definition
Hematologie	01042 14.0000	OTOAL 14.0 Term	Units		UL.		Orace 2	Crade 5	Cinc. 4		OTONE PLONE TURN DEMINION
Hemoglobin	Blood and lymphatic system	Anemia - Man	g/dL	12.2	17.7	<12.2 - 10.0	<10.0 - 8.0	<8.0	Life-threatening consequences; urgent intervention indicated	Death	A disorder characterized by an reduction in the amount of hemoglobin in 100 ml of blood. Signs and symptoms of anemia may include pallor of the skin and mucous membranes, shortness of
	disorders Blood and lymphatic system	Anemia - Woman	g/dL	9.5	15.8	<9.5 - 8.5	<8.5 - 7.5	<7.5	Life-threatening consequences; urgent intervention indicated	Death	include pallor of the skin and mucous membranes, shortness of breath, palpitations of the heart, soft systolic murmurs, lethargy, and fatigability.
	disorders CTC criteria	Anemia	g/dL			<lln -="" 10.0="" dl<="" g="" td=""><10.0 - 8.0	<8.0 g/dL transfusion indicated	Life-threatening consequences; urgent intervention indicated	Death		</lln>	<10.0 - 8.0	<8.0 g/dL transfusion indicated	Life-threatening consequences; urgent intervention indicated	Death	
Platelets	Investigations	Platelet count decreased	nb/µL	126 000	438 000	<126,000 - 75,000	<75,000 - 50,000	<50,000 - 25,000	<25,000	-	A finding based on laboratory test results that indicate a decrease in
	CTC criteria	Platelet count	nb/µL			<lln -="" 75,000<="" td=""><75,000 - 50,000	<50,000 - 25,000	<25,000		number of platelets in a blood specimen.	</lln>	<75,000 - 50,000	<50,000 - 25,000	<25,000		number of platelets in a blood specimen.
		decreased									
Leucocytes	Blood and lymphatic system disorders	Leukocytosis	nb/µL	3100	9100	-	-	>100,000	Clinical manifestations of leucostasis; urgent intervention indicated	Death	A disorder characterized by laboratory test results that indicate an increased number of white blood cells in the blood.
	CTC criteria	Leukocytosis	nb/μL	_				>100,000	Clinical manifestations of leucostasis; urgent intervention indicated	Death	
	Investigations	White blood cell decreased	nb/µL	3100	9100	<3100-2500	<2500 - 2000	<2000 - 1000	<1000/mm3	-	A finding based on laboratory test results that indicate an decrease in number of white blood cells in a blood specimen.
	CTC criteria	White blood cell decreased	nb/μL			<lln -="" 3000<="" td=""><3000 - 2000	<2000 - 1000	<1000	-		</lln>	<3000 - 2000	<2000 - 1000	<1000	-	
Biochimie									ļ		
Na - Sodium	Metabolism and nutrition disorders	Hypernatremia	mmol/L	128	145	>145 - 150	>150 - 155	>155 - 160 ; hospitalization indicated	>160 ; life-threatening consequences	Death	A disorder characterized by laboratory test results that indicate an elevation in the concentration of sodium in the blood.
	CTC criteria	Hypernatremia	mmol/L			<uln -="" 150<="" td="">>150 - 155	>155 - 160; hospitalization indicated	>160 ; life-threatening consequences	Death		</uln>	>150 - 155	>155 - 160; hospitalization indicated	>160 ; life-threatening consequences	Death	
	Metabolism and nutrition disorders	Hyponatremia	mmol/L	128	145	-	<128 - 125	<125 - 120	<120 ; life-threatening consequences	Death	A disorder characterized by laboratory test results that indicate a low concentration of sodium in the blood.
	CTC criteria	Hyponatremia	mmol/L			<lln -="" 130<="" td="">-	<130 - 120	<120 ; life-threatening consequences	Death		</lln>	-	<130 - 120	<120 ; life-threatening consequences	Death	
K - Potassium	Metabolism and nutrition disorders	Hypokalemia	mmol/L	3.6	5.1	<3.6 - 3.0	<3.6 - 3.0 ; symptomatic; intervention indicated	<3.0 - 2.5; hospitalization indicated	<2.5; life-threatening consequences	Death	A disorder characterized by laboratory test results that indicate a low concentration of potassium in the blood.
	CTC criteria	Hypokalemia	mmol/L			<lln -="" 3.0<="" td=""><3.6 - 3.0 ; symptomatic; intervention indicated	<3.0 - 2.5 ; hospitalization indicated	<2.5; life-threatening consequences	Death		</lln>	<3.6 - 3.0 ; symptomatic; intervention indicated	<3.0 - 2.5 ; hospitalization indicated	<2.5; life-threatening consequences	Death	
	Metabolism and nutrition disorders	Hyperkalemia	mmol/L	3.6	5.1	>5.1 - 5.5	>5.5 - 6.0	>6.0 - 7.0 ; hospitalization indicated	>7.0 ; life-threatening consequences	Death	A disorder characterized by laboratory test results that indicate an elevation in the concentration of potassium in the blood; associated
	CTC criteria	Hyperkalemia	mmol/L			>5.1 - 5.5	>5.5 - 6.0	>6.0 - 7.0; hospitalization indicated	>7.0 ; life-threatening consequences	Death	with kidney failure or sometimes with the use of diuretic drugs.
Bicarbonates			mmol/L	18	33	to be assessed as: • "normal",		mucaeu	consequences		
						 "abnormal not clinically signific 	ant" or (to be graded by the investigator a	nd declared as mild, moderate or s	severe)"		
Chloride			mmol/L	98	108	to be assessed as: • "normal",	I.			J.	
			_			"abnormal not clinically significant "abnormal clinically significant	ant" or (to be graded by the investigator a	nd declared as mild, moderate or s	severe)"		
Glucose	Metabolism and nutrition disorders	Hypoglycemia	mg/dL	73	118	<73 - 55	<55 - 40	<40 = 30	<30 ; life-threatening consequences; seizures	Death	A disorder characterized by laboratory test results that indicate a low concentration of glucose in the blood.
	CTC criteria	Hypoglycemia	mg/dL			<73 - 55	<55 - 40	<40 - 30	<30 ; life-threatening consequences; seizures	Death	
	Metabolism and nutrition disorders	Hyperglycemia	mg/dL	73	118	Fasting glucose value >118 - 160	Fasting glucose value >160 - 250	>250 - 500; hospitalization indicated	>500 ; life-threatening consequences	Death	A disorder characterized by laboratory test results that indicate an elevation in the concentration of blood sugar. It is usually an indication of diabetes mellitus or glucose intolerance.
	CTC criteria	Hyperglycemia	mg/dL				Fasting glucose value >160 - 250	indicated	>500 ; life-threatening consequences	Death	
Ca - Calcium	Metabolism and nutrition disorders	Hypercalcemia	mg/dL	8.0	10.3	>10.3 - 11.5	>11.5 - 12.5; symptomatic	>12.5 - 13.5; hospitalization indicated	>13.5; life-threatening consequences	Death	A disorder characterized by laboratory test results that indicate an elevation in the concentration of calcium (corrected for albumin) in blood.
	CTC criteria	Hypercalcemia	mg/dL			>10.3 - 11.5	>11.5 - 12.5 ; symptomatic	>12.5 - 13.5; hospitalization indicated	>13.5; life-threatening consequences	Death	
	Metabolism and	Hypocalcemia	mg/dL	8.0	10.3		<8.0 - 7.0 ; symptomatic	<7.0 - 6.0 ; hospitalization	< 6.0; life-threatening	Death	A disorder characterized by laboratory test results that indicate a low
	nutrition disorders		-	8.0	10.3			indicated	consequences		concentration of calcium (corrected for albumin) in the blood.
	CTC criteria	Hypocalcemia	mg/dL			<lln -="" 8.0<="" td=""><8.0 - 7.0 ; symptomatic	<7.0 - 6.0; hospitalization indicated	< 6.0 ; life-threatening consequences	Death		</lln>	<8.0 - 7.0 ; symptomatic	<7.0 - 6.0; hospitalization indicated	< 6.0 ; life-threatening consequences	Death	
Azote uréique sanguin			mg/dL	/	22	to be assessed as: • "normal", • "abnormal not clinically signific	cant" or				
Créatinine	Investigations	Creatinine increased	mg/dL	0.5	1.2	"abnormal clinically significant >1.2 - 1.8	(to be graded by the investigator a	nd declared as mild, moderate or s >3.6 - 7.2	>7.2		A finding based on laboratory test results that indicate increased
	CTC criteria	Creatinine increased	mg/dL			>1 - 1.5 x baseline; >ULN - 1.5 x	>15 - 3 0 v baseline: >15 - 3 0 v	>3.0 baseline; >3.0 - 6.0 x ULN	>6.0 x ULN		levels of creatinine in a biological specimen.
						ULN	ULN				
Alkaline phosphatase	Investigations	Alkaline phosphatase increased	U/L	48	164	>164 - 410	>410 - 820	>820 - 3280	>3280		A finding based on laboratory test results that indicate an increase in the level of alkaline phosphatase in a blood specimen.
	CTC criteria	Alkaline phosphatase increased	U/L			>ULN - 2.5 x ULN	>2.5 - 5.0 x ULN	>5.0 - 20.0 x ULN	>20.0 x ULN		
ALT (SGPT)	Investigations	Alanine aminotransferase increased	U/L	8	61	>61 - 183	>183 - 305	>305 - 1220	>1220		A finding based on laboratory test results that indicate an increase in the level of atanine aminotransferase (ALT or SGPT) in the blood
	CTC criteria	Alanine aminotransferase	U/L			>ULN - 3.0 x ULN	>3.0 - 5.0 x ULN	>5.0 - 20.0 x ULN	>20.0 x ULN		specimen.
AST (SGOT)	Investigations	increased Aspartate aminotransferase		14	60	>60 - 180	>180 - 300	>300 - 1200	>1200		A finding based on laboratory test results that indicate an increase in
(0301)		Aspartate aminotransferase increased	- OFL		ω.						A finding based on laboratory test results that indicate an increase in the level of aspartate aminotransferase (AST or SGOT) in a blood specimen.
	CTC criteria	Aspartate aminotransferase increased	e U/L			>ULN - 3.0 x ULN	>3.0 - 5.0 x ULN	>5.0 - 20.0 x ULN	>20.0 x ULN		
Bilirubine totale	Investigations	Blood bilirubin increased	mg/dL	0.2	2.2	>2.2 - 3.3	>3.3 - 6.6	>6.6 - 22.0	>22.0	-	A finding based on laboratory test results that indicate an abnormally high level of bilirubin in the blood. Excess bilirubin is associated with
	CTC criteria	Blood bilirubin increased	mg/dL			>ULN - 1.5 x ULN	>1.5 - 3.0 x ULN	>3.0 - 10.0 x ULN	>10.0 x ULN		jaundice.
Albumine	Metabolism and nutrition disorders	Hypoalbuminemia	g/dL	3.5	5.2	<3.5 - 3	<3 - 2	<2	Life-threatening consequences;	Death	A disorder characterized by laboratory test results that indicate a low
	CTC criteria	Hypoalbuminemia	g/dL			<lln -="" 3<="" td=""><3-2	<2	urgent intervention indicated Life-threatening consequences;	Death	concentration of albumin in the blood.	</lln>	<3-2	<2	urgent intervention indicated Life-threatening consequences;	Death	concentration of albumin in the blood.
Protéine Totale			g/dL	5.8	8.8	to be assessed as:			urgent intervention indicated		
			L			"normal", "abnormal not clinically signific "abnormal clinically significant	ant" or (to be graded by the investigator a	nd declared as mild, moderate or s	severe)"		
	CTC criteria	CTC differs from nouveless									
		CTC differs from nouvelles valeurs bio									
	-	-	-	-	-	-			1		1

Confidential Page 81 of 83

Protocol DNDi-FEX-09-HAT Version 3.0 Fexinidazole

Appendix 7 - Schedule of Study Events

Table 5 – Schedule of Events - Patients treated in hospital

Protocol-planned procedures and forms to be completed	Screening					Treatm	ent per	iod		In-ho	spital Follo	Follow-up period			
Timepoint →	D-15 to D-1	D1	D2	D3	D4	D5	D6	D7	D8	D9	D10	D11 (EoT)	D12	D13-D18 (EoH)	3 – 6 – 12 – 18 months
Rapid Diagnostic Test or CATT	х														
Detection of parasite in blood and/or lymph	Х											х			Х
Informed consent (before any additional medicines or study-specific procedures)	х														
Lumbar puncture (parasite and white blood cells in CSF)	х														x ¹
Pretreatment of helminthiasis ²	х														
Rapid Diagnostic Test and/or thick blood smear for diagnosis of malaria and, if necessary, treatment ²	х														
Karnofsky Performance Status	х											Х			Х
Inclusion and exclusion criteria	х														
Demographic data	х														
Medical history	х														
Signs and symptoms of HAT	х											х			Х
Vital signs ³	х								X ⁴			х		х	Х
Physical and neurological examinations	х								X ⁴			Х		х	Х
Haematology and biochemistry	х											х			X ⁵
Urine analysis	х											х			
Urine pregnancy test	X (D-1)											х			X (3 and 6 months only)
Triplicate ECG	x (D-1)				X D4 H4	X D4 H23	3					х			
Administration of fexinidazole		Х	Х	Х	Х	Х	Х	Х	Х	х	Х				
Blood sampling for PK analyses (specific patient groups)									X H3.15	Х Н3	X H3 H7.15	X D10H24	X D10H48		
Adverse event (AE) collection	X (if considered related to study participation)	х	х	х	х	х	х	х	х	х	х	х	х	х	X (If reasonable possibility of relation to treatment)
Serious adverse event (SAE) collection from signature of consent form to last study visit	х	Х	х	х	х	х	х	х	х	х	х	х	х	х	х
Collection of concomitant medication	х	Х	Х	Х	х	Х	х	х	х	х	Х	Х	х	Х	

Page 82 of 83

Confidential

¹ At 3 months, only if indicated by patient's clinical status.

² Treatment according to national guidelines.

³ Temperature, blood pressure, heart rate and respiratory frequency.

⁴ Only if indicated by patient's clinical status.

⁵ At 3 and 6 months. At 12 and 18 months only if indicated by patient's clinical status.

Protocol DNDi-FEX-09-HAT Version 3.0 Fexinidazole

Table 6 – Schedule of Events - Patients treated on an out-patient basis

Protocol-planned procedures and forms to be completed ${\sf Timepoint} \ \to $	Screening D-15 to D-1	Dispensing D0	Treatment period										Follow-up period	
			D1	D2	D3	D4	D5	D6	D7	D8	D9	D10	D11 (EoT)	3 – 6 – 12 – 18 months
Rapid Diagnostic Test or CATT	х													
Detection of parasite in blood and/or lymph	x												Х	х
Informed consent (before any additional medicines or study-specific procedures)	х													
Lumbar puncture (parasite and white blood cells in CSF)	Х													x ¹
Pretreatment of helminthiasis ²	х													
Rapid Diagnostic Test and/or thick blood smear for diagnosis of malaria and, if necessary, treatment ²	х													
Karnofsky Performance Status	х												х	х
Inclusion and exclusion criteria	х													
Demographic data	х													
Medical history	х													
Signs and symptoms of HAT	х												х	Х
Vital signs ³	х												Х	Х
Physical and neurological examinations	х												х	х
Haematology and biochemistry	х												х	X ⁴
Urine analysis	x												Х	
Urine pregnancy test	X (D-1)												х	X (3 and 6 months only)
Triplicate ECG	X (D-1)												х	
IMP dispensing / Discharge from hospital		х												
Administration of fexinidazole			х	х	х	х	х	х	х	х	х	х		
Blood sampling for PK analyses													X D10H24 ⁵	
Assessment of understanding of instructions for treatment (questionnaire)		Х												
Treatment compliance (interview)													Х	
Acceptability of packaging (questionnaire)													Х	
Adverse event (AE) collection	X (if considered related to study participation)												X (interview)	X (If reasonable possibility of relatio to treatment)
Serious adverse event (SAE) collection from signature of consent form to last study visit	•													-
Collection of concomitant medication	х												X (interview)	

¹ At 3 months, only if indicated by patient's clinical status.

² Treatment according to national guidelines.

³ Temperature, blood pressure, heart rate and respiratory frequency.

⁴ Only if indicated by patient's clinical status.

⁵ Additional sampling for PK may be performed between Day 1 and Day 11 if the patient returns to the centre for an unscheduled visit

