4.2. Non-inclusion Criteria

To be included in the study, the patient must not fulfil any of the following exclusion criteria:

- Active clinically relevant medical conditions other than HAT that, in the Investigator's opinion, could jeopardise patient safety or interfere with participation in the study, including but not limited to significant liver and cardiovascular diseases, HIV infection, CNS trauma or seizure disorders, coma or altered consciousness not related to HAT;
- Severe renal or hepatic impairment defined as:
 - elevated creatinine at > 3 times the upper limit of normal (ULN);
 - elevated ALT, AST or bilirubin at > 3 X ULN;

Confidential Page 26 of 83

- Severely deteriorated general condition, such as cardiovascular shock, respiratory distress, or terminal illness;
- Any condition (except symptoms of HAT) that compromises ability to communicate with the Investigator as required for completion of the study;
- Any contraindication to imidazole products (known hypersensitivity to imidazoles);
- Treatment for HAT within 2 years prior to inclusion;
- Prior enrolment in the study or prior intake of fexinidazole;
- Foreseeable difficulty in complying with the schedule of follow-up visits (migrants, refugees, itinerant traders, etc.).

The following criteria are considered as temporary non-inclusion criteria:

- Recovery period after antimalarial treatment and/or treatment of helminthiasis (at least 3 days);
- Uncontrolled diabetes or hypertension or any patients requiring clinical stabilisation; wait until appropriate treatment to control the disease has been initiated:
- First trimester of pregnancy (based on date of last menstrual period);
- Traumatic lumbar puncture at Screening i.e. red blood cells visible in CSF; wait for 48 hours before repeating lumbar puncture.

Ineligible patients will be treated according to the protocol of the National HAT Control Program (PNLTHA) and will receive the same support from the Sponsor during the treatment period.

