5.6. Concomitant Treatment

5.6.1. Malaria

All patients will undergo a thick blood smear and/or rapid diagnostic test (RDT) to detect malaria at Screening. All patients with a positive result will receive treatment.

Prior to starting treatment with fexinidazole, malaria will be treated for 3 days with the combination artemether-lumefantrine (Coartem®) unless the patient has personal contraindications, such as severe malaria or hypersensitivity to one of the components, i.e. artemether or lumefantrine. All of the existing artemisinin-based combination therapies used against malaria have effects on the QT interval. Coartem® was chosen because its effects on QT-interval prolongation are known

Confidential Page 29 of 83

to be moderate and well quantified (9). The choice was made to minimise confounding factors in the assessment of fexinidazole-related QT-interval prolongation. Coartem® will be provided free of charge by the Sponsor.

In patients with a contraindication to Coartem[®], the Investigator can choose another antimalarial agent. The choice must be recorded in the CRF.

Treatment will be followed by a recovery period of at least 3 days between the last dose of Coartem[®] and the start of treatment with fexinidazole.

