6.2.2. Baseline Assessment

Whether the patient is being considered for treatment in hospital or as an out-patient, the following procedures will be performed between Day -15 and Day -1 in order to stage the disease, to collect medical history and safety data, and to check the inclusion and non-inclusion criteria.

- Collection of informed consent / assent prior to administering any additional medication or to performing any non-routine assessment;
- Collection of CSF sample for WBC and disease staging;
- Karnofsky Performance Status,
- Review of inclusion and non-inclusion criteria
- Collection of demographic data;
- Collection of full medical history;
- Collection of signs and symptoms of HAT, in particular severity and time since the start of symptoms;
- Vital signs: body temperature, blood pressure, heart rate and respiratory rate;
- Diagnosis of malaria using RDT and/or thick blood smear and, if the result is positive, administration of antimalarial treatment;
- Treatment of helminthiasis, according to routine practices;
- Collection of concomitant medication;
- Physical and neurological examinations;

Confidential Page 34 of 83

- Laboratory safety assessments (see Appendix 3 Laboratory Tests; p 75) when possible, samples will be collected in the morning from patients in the fasting state;
 - Haemoglobin;
 - o Haematology: WBC, platelet count;
 - Biochemistry: albumin, alkaline phosphatase (ALP), alanine aminotransferase (ALT), aspartate aminotransferase (AST), blood urea nitrogen (BUN), chloride, creatinine, glucose, potassium, sodium, calcium, total bilirubin, bicarbonates and total protein;
 - Urine analysis (leucocytes, nitrites, pH, protein, glucose, ketone bodies, urobilinogen, bilirubin, blood and haemoglobin);
- Urine pregnancy test for women of child-bearing potential, to be done on Day -1;
- Triplicate digital ECG (CarTouch®), to be done on Day -1;
- Collection of SAEs.

6.3. IMP Dispensing: Day 0

If the patient is to be treated on an out-patient basis, the following procedures will be performed before s/he returns home to begin treatment.

- Check that all procedures for baseline assessment have been performed.
- Dispensing of IMP and, before returning home, reminder concerning instructions for taking the IMP and interview with Investigator to collect responses to questionnaire and ensure good understanding of the instructions by the patient and/or the caregiver;
- Collection of SAEs since signature of informed consent.

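### The schedules of events defer malaria treatment to national guidelines, Section 5.6.1 names one antimalarial (unless contraindicated) to protect the QT assessment, and nothing says which governs

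*Protocol*

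**What the plan says.** Protocol Section 5.6.1 is specific. Before fexinidazole, "malaria will be treated for 3 days with the combination artemether-lumefantrine (Coartem®) unless the patient has personal contraindications". It notes that the existing artemisinin-based "combination therapies used against malaria have effects on the QT interval", that the effect of the named product is moderate and has been well measured, and gives its purpose: "The choice was made to minimise confounding factors in the assessment of fexinidazole-related QT-interval prolongation". The one departure it allows is for a patient with a contraindication, where "the Investigator can choose another antimalarial agent. The choice must be recorded in the CRF".

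The schedules of events in Appendix 7 give a different instruction. In Table 5 (in-patients) and Table 6 (out-patients) the row "Rapid Diagnostic Test and/or thick blood smear for diagnosis of malaria and, if necessary, treatment" carries footnote 2, which says "Treatment according to national guidelines". The same footnote serves the helminthiasis row.

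Section 6.2.2 asks for antimalarial treatment after a positive test without naming an agent. It also sets the reference recording: "Triplicate digital ECG (CarTouch®), to be done on Day -1". Section 6.4.2 adds two triplicate recordings for patients treated in hospital, 4 hours and 23 hours after the Day 4 dose. Both cohorts have a Day 11 ECG.

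**The concern.** The footnote and Section 5.6.1 are both operative instructions for the same act, and they differ. One names an agent, with one exception and a stated statistical reason. The other points to a standard outside the protocol and mentions neither the agent, nor the contraindication condition, nor Section 5.6.1. The study runs in the DRC and Guinea, so the footnote refers to more than one national standard.

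A schedule of events is often used as the working checklist at a site. Someone following it could give an antimalarial other than the named one to a patient with no contraindication, and would be complying with the protocol as written in Appendix 7. The Day -1 ECG follows that treatment and is the natural reference for the later recordings. Any residual QT effect of the antimalarial would raise the baseline and make the change on fexinidazole look smaller. If agents varied between patients or countries, so could that shift, and there is no control arm against which to separate it. Limiting that variation is the purpose Section 5.6.1 states for its choice.

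**Working it through.** The plan has no figure to reproduce here. The check is a comparison of passages and a day count.

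**Passages side by side**

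| Place | Agent named? | Condition for another agent | Refers to 5.6.1? |
|---|---|---|---|
| Section 5.6.1 | Yes, artemether-lumefantrine for 3 days | Contraindication only; choice recorded in the CRF | – |
| Section 6.2.2 | No | None stated | No |
| Table 5, footnote 2 | No; national guidelines | None stated | No |
| Table 6, footnote 2 | No; national guidelines | None stated | No |

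No passage sets an order of precedence between the schedule and the treatment section.

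**Interval from last antimalarial dose to the Day -1 ECG**

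Inputs: a recovery period of at least 3 days before fexinidazole (Section 4.2 for any antimalarial, Section 5.6.1 for the named one); first fexinidazole dose on Day 1; baseline ECG on Day -1; screening from Day -15 to Day -1. The result depends on whether the calendar contains a Day 0 (Table 6 has one, Table 5 does not) and on whether the 3 days are counted as three clear days or as a difference of three days.

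| Calendar | Counting of the 3 days | Latest last dose | Gap to Day -1 ECG |
|---|---|---|---|
| No Day 0 | Three clear days (-3, -2, -1) | Day -4 | 3 days |
| No Day 0 | Difference of three days | Day -3 | 2 days |
| With Day 0 | Three clear days (-2, -1, 0) | Day -3 | 2 days |
| With Day 0 | Difference of three days | Day -2 | 1 day |

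At minimum recovery the gap is therefore 1 to 3 days, and the baseline ECG is recorded before the recovery period has ended, because that period runs to the first fexinidazole dose and not to the ECG. At the other extreme, a 3-day course starting on Day -15 ends on Day -13, and the gap is 13 - 1 = 12 days. In every case the antimalarial comes before the baseline ECG.

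**Which recordings could be affected**

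In-patients have planned ECGs on Day -1, after the Day 4 dose (4 h and 23 h) and on Day 11. Out-patients have Day -1 and Day 11 only. Only malaria-positive patients given an agent other than the one in Section 5.6.1, without a contraindication, would be affected by the discrepancy. The documents give neither the malaria-positive share nor the content of the two countries' guidelines, so that number cannot be calculated.

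**The case against.** The strongest reply is that the two texts may come to the same thing. If the guidelines of both countries lead to the agent named in Section 5.6.1, the footnote changes nothing. That stands: neither guideline is in the documents, so a practical difference is possible but not shown.

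The body of the protocol also limits the risk. The sponsor supplies the named agent free of charge (5.6.1). The recovery period applies to any antimalarial (4.2). Medicines taken in screening are recorded in the CRF (5.6.4), and the SAP plans a listing of malaria pre-treatment (Section 9.1, listing 5.5). A departure would be traceable. This stands too, but it does not say which instruction a site should follow.

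Three stronger readings are tempting and are not supported:

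- A reader might infer that the footnote is what puts a QT-active drug before the baseline ECG. Section 5.6.1 itself says that all the combinations affect QT, so malaria-positive patients have such a drug before Day -1 even with full adherence. The footnote could add only variation between agents.
- A reader might size the problem by assuming a malaria share. An assumed 10% to 50% of 174 gives 0.10 × 174 = 17 to 0.50 × 174 = 87 patients. The share is not in the documents, and the product counts everyone treated for malaria, including those given the named agent.
- A reader might conclude that the analysis neglects antimalarial exposure. The SAP (6.3.3, 8.8.4) places ECG analysis in a separate plan that is not among the documents, so an adjustment or split by antimalarial cannot be called missing.

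Finally, QT change is not among the safety endpoints of Section 2.2.2, and Section 9.6.1 plans only to describe Day 11 ECG abnormalities. That lowers the weight of the point, although Sections 5.6.1 and 6.4.2 show that a QT assessment is intended.

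**Conclusion.** The inconsistency is real. Footnote 2 in both schedules and Section 5.6.1 give different instructions for the treatment of malaria, Section 6.2.2 does not settle it, and no text says which prevails. What it puts at risk is narrow: consistency of the antimalarial given before the Day -1 ECG, which the protocol itself presents as a guard against QT confounding.

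The consequence is conditional. It requires that a national guideline leads to another agent and that a site follows the footnote instead of Section 5.6.1. The number of patients affected is unknown and may be zero. The Day 4 recordings concern in-patients only, and the primary effectiveness endpoint is unaffected. Severity: minor. No view is taken here on which treatment rule is right.

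**What to change.** The sponsor should reconcile footnote 2 with Section 5.6.1: give the malaria row its own footnote in Tables 5 and 6, separate from the helminthiasis row, and state which passage governs. The cost is one footnote in two tables. SAP Section 11 already records a change after database lock, so if enrolment is closed the same purpose is served by stating in the study report which rule the sites were told to follow.

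Optionally, confirm that the separate ECG analysis plan accounts for the antimalarial received in screening. The malaria pre-treatment data are already to be listed, so no new data collection is needed. If results are split by agent, some groups will be small and should be read descriptively.
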